Background: In recent years, various methodologies have been introduced to enhance the outcomes of scaling and root planing (SRP), with the intent of potentially eliminating the necessity for periodontal surgical interventions under specific circumstances. Noteworthy among these novel approaches are the utilization of non-steroidal anti-inflammatory drugs (NSAIDs) and herbal remedies like Aloe Vera. This present study endeavors to clinically assess the impact of flurbiprofen gel in contrast to Aloe Vera gel, as supplementary agents to SRP, in the elimination of periodontal pocket depths among individuals afflicted by stage III chronic periodontitis, particularly focusing on the subset of smoking patients. **Materials and Methods:** In this study, 60 patients with stage III/grade C periodontitis were enrolled. They were divided into three groups using the split mouth method: Group one (G1), which received Flurbiprofen and placebo, Group two (G2), which received Aloe Vera and placebo, and Group three (G3), which received Flurbiprofen and Aloe Vera. At the baseline, the fourth, eighth-, twelfth weeks and six months following treatment, the plaque index (PI), gingival index (GI), bleeding on probing (BOP), clinical attachment level (CAL), and probing depth (PD) were all measured. **Statistical Analysis:** Statistical analysis was done using SAS 9.4 Software (SAS Institute Inc., Cary, NC, USA). Means and standard deviations (SD) were calculated for all continuous variables (periodontal parameters: CAL, PD, BOP, GI, PI) at the baseline, fourth week, eighth week, and twelfth week and 6 months.

Keywords: periodontitis, flurbiprofen, aloe vera, root planing.

Introduction:

Inflammation and periodontal tissue destruction is a consequence of periodontal pockets originating from chronic periodontitis. [1] The latter is an infectious disease resulting from the interaction between the invasion of biofilm microorganisms and periodontal immune response in a vulnerable host. [2]

During periodontal attachment loss, PGE2 production levels primarily by macrophages and fibroblasts are increased in the tissues and gingival crevicular fluid (GCF). [3,4] PGE2 promotes the release of MMPs, in addition to osteoclastic bone resorption, and it play a significant role in the alveolar bone loss observed in periodontitis. [5]

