30] Aloe Vera also inhibits the cyclooxygenase pathway, dropping the production of prostaglandins, thus decreasing the inflammation. [31]

Some studies stated the use of aloe Vera in dentistry in numerous areas like disinfecting dental unit water network, [32] gutta-percha sterilization, [33] antiseptic effect on candida albicans, [34] Aphthous stomatitis management, [35] as an ingredient in toothpastes [36-37] and mouthwashes.[28] Up to date, limited studies have been reported in relation to the effect of topical application of aloe Vera in the periodontal pocket for periodontal disease management. [38]

The null hypothesis is that flurbiprofen has no statistically significant effect in comparison to Aloe Vera gel as an adjunctive to SRP in the reduction of periodontal pockets in smoking patients with chronic periodontitis stage III.

Aim of this study:

This study aims to evaluate clinically the effect of flurbiprofen gel in comparison to Aloe Vera gel as adjunctive to SRP in the reduction of periodontal pockets in patients with chronic periodontitis stage III in smoking patients.

Materials and methods:

Participants:

This study was conducted at the Department of Oral Surgical Sciences, Division of Periodontology, Faculty of dentistry, Beirut Arab University (BAU)-Lebanon after approval of Institutional Review Board (IRB) with trial NO 2022-H-0100-D-R-0487. Patients were first briefed about the study and written consent was obtained. The study was performed in compliance with the principles of the Declaration of Helsinki.

The estimated sample size will be calculated according to <http://epitools.ausvet.com.au/>, by taking the means of clinical attachment level at 3 months in both groups from a previous similar study conducted by (39) where mean for test site = 5.75 ± 0.35 and mean for control site is = 6.4 ± 0.3 , where the variance will be calculated to be 0.35, assuming a confidence level of 95% and a study power of 80%. The calculated sample size will be 14 patients per group (28 operating sites). However, as some dropouts may be expected, a minimum of 20 patients per group were recruited

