Inclusion criteria: 60 patients were selected who had clinical periodontal loss and radiographic bone loss of stage III/grade C with no history of systemic disease. They had at least 2 periodontal sites with a pocket depth of six mm or greater, radiographic evidence of bone loss extending to the middle third of the root, and clinical attachment loss of five mm or more. Eligible subjects were categorized as current smokers if they consistently smoked more than 10 cigarettes per day for a minimum of 5 years. Additionally, individuals with no record of undergoing any periodontal treatment within the six months preceding the study were considered for inclusion. These stringent criteria aimed to ensure a relevant and homogeneous patient cohort for the research investigation.

Exclusion criteria: Patients with systemic illnesses such as diabetes mellitus or conditions that could potentially impair wound healing were excluded from participation. Additionally, individuals who were pregnant or lactating were not considered for inclusion in the study. Subjects who had been prescribed systemic antibiotics or non-steroidal anti-inflammatory drugs (NSAIDs) within the three months preceding the study were also excluded. Furthermore, individuals with confirmed or suspected hypersensitivity to Flurbiprofen or aloe Vera, the focus of the investigation, were not included in the study population. These stringent exclusion criteria aimed to control for potential confounding factors and establish a well-defined and relevant patient group for the research analysis.

Clinical protocol

Initial therapy was performed on all patients and consisted of full mouth scaling and root planing on 2-4 sessions, by hand and ultrasonic instrumentation, with oral hygiene instructions reinforcement and proper brushing technique (modified Bass technique) instructions. Note that patients received the same toothbrushes, toothpaste, and interdental brushes. Oral hygiene was reinforced at every visit.

The selected patients were allocated into three groups (each containing 20) with the help of a computerized randomizer (Randomizer.org), and using a split mouth design, sites were randomly allocated for each patient into either test or control group using a coin flip method:

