- Group one (G1): comprised of 20 patients who received treatment involving the application of flurbiprofen gel as an adjunct to scaling and root planing. Specifically, on the test site of each patient, one milliliter of 2.5% flurbiprofen gel was applied, while on the contralateral side, scaling and root planing were performed as the control intervention.
- Group two (G2): comprised of 20 patients who received treatment involving the application of aloe Vera gel as an adjunct to scaling and root planing. Specifically, on the

test site of each patient, one milliliter of 98% aloe Vera was applied, while on the contralateral side, scaling and root planing were performed as the control intervention.

- Group three (G3): The intervention involved applying flurbiprofen gel on one site, while the contralateral side received an application of 98% aloe vera.

Clinical measurements:

The clinical periodontal parameters were recorded by one blinded examiner from the mesio-buccal, mid-buccal, disto-buccal, disto-lingual, mid-lingual, and mesio-lingual surfaces of each tooth using a colour coded periodontal probe (PQWBR - Hu Friedy Mfg. Inc. Chicago, IL, USA): and checked by another blinded examiner. Examiners were calibrated to ensure intra-examiner as well as inter-examiner agreement when measuring PD and CAL values. Fifteen patients were examined twice before the trial, 24 hours apart. Calibration was considered accepted if both measurements at the baseline and after 24 hours were similar to one mm at the 90% level.

In this clinical study, various clinical measurements were undertaken to assess the oral health status of the participants. These measurements included the clinical attachment level (CAL), probing depth (PD), plaque index (PI), gingival index (GI), and bleeding on probing (BOP).

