Initially, the PI and GI were measured at four sites per tooth, with gingival bleeding being recorded within 15 seconds. To prevent misinterpretation of gingival bleeding as BOP, patients were asked to rinse with water after this assessment. Subsequently, all teeth were probed at six different locations per tooth. CAL was determined as the distance from the cemento-enamel junction (CEJ) to the pocket depth, while the PD was measured as the distance from the gingival margin to the base of the pocket. BOP was recorded 15 seconds after probing. It is important to note that these clinical parameters were recorded at the baseline (1st visit) before the treatment and were repeated at the fourth week (2nd visit), eighth week (3rd visit), twelfth week (fourth visit), and at 6 months (5th visit). During this observation period, participants received reinforcement of plaque control and additional instructions to maintain optimal oral hygiene

Preparation of gels:

Aloe Vera:

Aloe vera gel used in this study was 98% aloe vera[®] gel concentration (Avivir; Denmark) and 2% normal saline. Commercial preparation method of 98% concentration of aloe vera gel was washing the ripe aloe Vera leaves thoroughly under water and cutting off their skin. Each leaf was cut into several pieces and seeping gel from the pieces were collected in a sterile container and stored at 4°C until the time of application. [38]

Flurbiprofen:

Gel was made of 20% poloxamer and 10% ethanol as an Optimum formulation with sustained release up to 48 hours and a reasonable sol gel transition phase.

Statistical analysis:

Statistical analysis was done using SAS 9.4 Software (SAS Institute Inc., Cary, NC, USA). Means and standard deviations (SD) were calculated for all continuous variables (periodontal parameters: CAL, PD, BOP, GI, PI) at the baseline, fourth week, eighth week, and twelfth week and 6 months. Repeated linear mixed-effects models (PROC MIXED in SAS) were used to examine the changes in all periodontal parameters over the five-time points within each group and between groups. An unstructured covariance matrix was used, residual plots were visually reviewed to check model fit, and extreme outliers were eliminated using the restricted likelihood distance. A Tukey-Kramer 8 correction was applied to all pairwise comparisons. One-way ANOVA was used to examine group differences in PD reduction and CAL. A p-value of 0.05 was considered statistically significant.

References:

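### The side treated within each mouth is set by coin flip with no stated concealment, timing, record or independent allocator, so repeated or overridden flips cannot be excluded or audited

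*Combined protocol and SAP*

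**What the plan says.** All places are in the combined protocol and SAP.

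- **Allocation (Clinical protocol).** Patients are divided into three groups of 20 by an online computerized randomizer. Within the mouth, "sites were randomly allocated for each patient into either test or control group using a coin flip method". The text names no allocator, time, record, witness or concealment for the flip.
- **SRP (Clinical protocol).** Initial therapy in all patients "consisted of full mouth scaling and root planing on 2-4 sessions, by hand and ultrasonic instrumentation", and this is described before allocation. The G1 and G2 descriptions then say that the test site received gel, "while on the contralateral side, scaling and root planing were performed as the control intervention".
- **Group three.** One site receives flurbiprofen and the contralateral side aloe vera, so there is no control site. The text does not say what a test-or-control flip decides there.
- **Blinding (Clinical measurements).** "The clinical periodontal parameters were recorded by one blinded examiner", with a second blinded examiner checking. Nothing is said about the operator or the patient.
- **Baseline (Clinical measurements).** "these clinical parameters were recorded at the baseline (1st visit) before the treatment".
- **Placebo.** The abstract describes "Group one (G1), which received Flurbiprofen and placebo", and likewise a placebo in G2. The group descriptions under Clinical protocol mention none.
- **Analysis (Statistical analysis).** Mixed models of change over five time points and a one-way ANOVA of PD reduction and CAL. No adjustment for the site's baseline value is named.

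**The concern.** In a split-mouth trial the side allocation is the randomization that protects the within-patient comparison. Here it decides gel against SRP alone in G1 and G2, and flurbiprofen against aloe vera in G3. G3 is the only within-patient test of the two gels named in the aim and null hypothesis.

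A pre-generated list can be compared afterwards with what was done. A coin flip leaves no such list, and no log is described. Since baseline is charted before treatment, whoever flips may already know which pocket is deeper. Eligibility asks for at least two sites, and no rule fixes which pair is studied before the flip.

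Two biases therefore cannot be excluded. The flip may be repeated or overridden so that a preferred site gets the gel. Or an operator who knows the side may instrument the two sides unequally. Blinded examiners protect the reading of the outcome, but neither the allocation nor the instrumentation.

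**Working it through.** **Order of events.** The initial-therapy paragraph puts full-mouth SRP before the allocation sentence. If that is the sequence, both sides were instrumented before any side was assigned. The G1 and G2 descriptions name SRP of the contralateral side as the control intervention, which can mean either SRP done at the gel visit or simply SRP alone. The text does not settle which.

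**The plan's own figure.** Under Participants, CAL at 3 months is "mean for test site = 5.75 ± 0.35 and mean for control site is = 6.4 ± 0.3", a difference of 6.4 − 5.75 = 0.65 mm. With the stated variance of 0.35, 95% confidence (taken as two-sided) and 80% power:

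n = 2 × (1.960 + 0.842)² × 0.35 / 0.65² ≈ 13.0, just above 13, so 14 per group.

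The stated 14 is reproduced. The SD this implies is √0.35 = 0.59 mm.

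**Illustrative baseline shift.** None of the following assumptions is in the document: the SD also applies at baseline; the between-site correlation ρ is 0 to 0.5; the net excess is 20%, so the preferred site gets the gel in 60% of patients and the other in 40%.

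Mean absolute gap between two sites = 2 × SD × √(1 − ρ) / √π. Shift = 0.20 × gap.

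| SD (mm) | ρ | Gap (mm) | Shift (mm) | Share of 0.65 mm |
|---|---|---|---|---|
| 0.59 | 0 | 0.666 | 0.133 | 20.5% |
| 0.59 | 0.5 | 0.471 | 0.094 | 14.5% |
| 0.35 | 0 | 0.395 | 0.079 | 12.2% |
| 0.35 | 0.5 | 0.279 | 0.056 | 8.6% |
| 1.0 | 0 | 1.128 | 0.226 | 34.7% |
| 1.0 | 0.5 | 0.798 | 0.160 | 24.6% |

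On the plan's variance the shift is about 0.09 to 0.13 mm, and those rounded figures are 14% and 20% of 0.65 mm. The shift is proportional to the assumed net excess.

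**Carry-over to the outcome.** Suppose the baseline-to-follow-up correlation is 0.7 (assumed). A baseline shift then passes into the follow-up value at 0.7 of its size. It passes into change from baseline at 0.3 of its size, in the opposite direction. The 20% case gives 0.3 × 0.094 = 0.028 mm to 0.3 × 0.133 = 0.040 mm on change, about 4% to 6% of 0.65 mm.

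**Type I error.** Simulation of 20,000 trials of 20 pairs with no true effect, SD √0.35, between-site correlation 0.5 and baseline-to-follow-up correlation 0.7. A fraction f of unwanted flips is repeated once, so P(preferred) = 0.5 + 0.25f, with the shallower site preferred.

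| f | P(preferred) | Bias, follow-up (mm) | Type I error, follow-up | Bias, change (mm) | Type I error, change |
|---|---|---|---|---|---|
| 0 | 0.50 | 0.002 | 0.050 | 0.001 | 0.052 |
| 0.5 | 0.625 | −0.081 | 0.076 | 0.036 | 0.057 |
| 1 | 0.75 | −0.163 | 0.166 | 0.072 | 0.080 |

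**Could it be detected afterwards?** An exact two-sided binomial check of how often the gel went to the preferred site needs at least 15 of 20, or 39 of 60, in one direction. With f = 0.5 it would flag the problem with probability 0.18 at n = 20 and 0.40 at n = 60. With f = 1 the probabilities are 0.62 and 0.97. A count made after the event is a weak safeguard against moderate override in a group of 20.

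**The case against.** A fair coin is a valid and unpredictable way to generate an allocation, and a flip can be witnessed and logged. What is missing may be description rather than conduct. Group assignment is computerized, outcomes are read by calibrated, blinded examiners, and study sites must have pockets of at least 6 mm, which narrows the room for selection. The planned analysis looks largely at change, where the effect of a baseline shift is smaller. All of this stands and limits the harm. It does not supply the missing allocator, timing, record or concealment, and the 6 mm criterion has no upper bound.

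A reader might infer more than the text supports:

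- **That the operator flips at the chair, unconcealed.** The document gives neither place nor person. What can be said is that no concealment is described.
- **That the operator knew the side while instrumenting.** This is possible but not established, because full-mouth SRP is described before allocation. The G3 text describes no SRP step at gel placement.
- **That flips were in fact repeated.** Nothing in the document indicates this.
- **That a chance left-right imbalance is a flaw.** Nothing suggests that left or right is prognostic, and with a fair flip an uneven split does not bias the within-mouth contrast.
- **That the shift is nearer a third of the sizing difference.** With the same 20% excess, that needs a gap of about 1 mm between paired sites (0.2 / 0.65 = 31%). The document gives no such gap, and the plan's variance implies 0.47 to 0.67 mm.

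**Conclusion.** The point holds as a gap in safeguards, not as a demonstrated bias. The allocation behind every within-mouth contrast has no stated concealment, timing, record or independent person, so repetition or override cannot be excluded or audited. Uneven instrumentation cannot be excluded either, while the two descriptions of SRP remain unreconciled.

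If a 20% net excess occurred, the baseline contrast would move by about 0.09 to 0.13 mm (14% to 20% of 0.65 mm) on the plan's variance, and change from baseline by less. These sizes rest on assumed override rates, SDs and correlations, and are not estimates of what happened. The change should be made because it costs little. It does not by itself invalidate the trial.

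**What to change.** **If any allocation remains to be done.** Generate the side list with the same computerized randomizer, by simple randomization or undisclosed blocks of varying size. Do not force 10 left and 10 right in each group of 20: an operator who sees the assignments could then deduce the last ones. For G3, state that the list decides which side receives flurbiprofen. Have existing staff who do not treat the patient hold the list in sequentially numbered opaque envelopes. Fix the pair of study sites first. Open each envelope only after both sites are charted and SRP of both is complete, and log the opening.

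**If allocation is already done**, as the past tense of the conduct text suggests:

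- State how, when and by whom the flip was made, whether it was recorded, and what it decided in G3.
- Report baseline PD and CAL by site treatment within each group. Baseline means and SDs are already planned, so only the breakdown is new.
- Adjust the within-mouth comparisons for site baseline, for example as a covariate in the mixed model with the four later visits as the outcome. This addresses imbalance in measured depth but cannot repair uneven instrumentation.

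**In either case**, reconcile the two descriptions of when SRP was done relative to allocation, and the abstract's placebo with the group descriptions. Also state whether the operator was blinded.

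**Cost.** One list and 60 envelopes prepared by existing staff, one opened at each gel placement. Sample size is unchanged (14 calculated, 20 recruited per group). The reporting route needs one extra table and a covariate.

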Smoking has been identified as a major risk factor in the development and progression of periodontal disease. Epidemiological studies have presented a significantly higher risk for periodontal disease in smokers compared to non-smokers, and the increased risk is proportional to the duration and rate of smoking (Eke et al., 2016).[6]

The first main goal during the treatment of periodontal disease is eliminating microbial source and causative factors, thus preventing further progression of the disease and maintaining periodontal tissue health. [7] Surgical and non-surgical modalities are available for the treatment of periodontal diseases. [7] The non-surgical option consisting of mechanical debridement of the tooth surface with scaling and root planning (SRP), [8] improves pocket depth (PD) and increases clinical attachment level (CAL) to some extent, [9]

However, mechanical debridement alone may not be enough in patients with deep periodontal PD or having areas of furcation involvements. [10] Some pathogens like *Actinobacillus actinomycetemcomitans*, *Porphyromonas gingivalis*, *Prevotella Intermedia*, *Bacteroides forsythus*, *peptostreptococci* micros may not be eliminated as a result of the limited access in deep subgingival areas, thus increasing the risk of treatment failure. [10]

Research have shown the significance of PGE2 in the development of periodontal diseases, [11]and since prostaglandins are inhibited by nonsteroidal anti-inflammatory drugs (NSAIDs), [12] researchers have explored the possible use of NSAIDs as possible host–response modulators in the treatment of periodontal disease.[13] However, achieving noticeable periodontal improvements requires daily administration of NSAIDs for extended periods which may lead to undesirable side effects gastrointestinal (GI), renal, cardiovascular (CV), cerebrovascular, and central nervous system (CNS) adverse effects [14]

It is advised to consider using local drug delivery (LDD) as an adjunct to conventional periodontal therapy to reach the best clinical outcomes. LDD is an effective method of delivering drugs. Higher drug concentrations at the targeted area can be reached using LDD with a lower drug dose than the usual systemic delivery and thus fewer side effects. [15]

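### Within-group change from baseline has the same inferential weight as the randomised comparisons, but it cannot separate a gel effect from SRP and hygiene

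*Combined protocol and SAP*

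**What the plan says.** The Statistical analysis section states that mixed models "were used to examine the changes in all periodontal parameters over the five-time points within each group and between groups". A Tukey-Kramer "correction was applied to all pairwise comparisons", and "A p-value of 0.05 was considered statistically significant". A separate sentence adds: "One-way ANOVA was used to examine group differences in PD reduction and CAL". No primary outcome, time point or contrast is named, and within-group change is not labelled descriptive.

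Four other parts of the plan bear on how a change from baseline can be read:

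- **Inclusion criteria:** of the patients, "They had at least 2 periodontal sites with a pocket depth of six mm or greater".
- **Clinical protocol:** all patients receive full-mouth SRP, and oral hygiene is reinforced at every visit. G1 and G2 pair a gel site with a contralateral SRP control site, allocated by coin flip. G3 has flurbiprofen on one side and aloe vera on the other.
- **Clinical measurements:** baseline is recorded before treatment, with follow-up at weeks 4, 8 and 12 and at 6 months.
- **Introduction:** SRP by itself "improves pocket depth (PD) and increases clinical attachment level (CAL) to some extent".

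The aim and the null hypothesis are comparative: flurbiprofen against aloe vera, each as an adjunct to SRP.

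**The concern.** An adjunctive effect is what the gel adds to SRP. A test of change over time within a group measures SRP, better plaque control, any regression to the mean and the gel together. The plan itself expects the first of these to be favourable. A small within-group p-value is therefore likely in every group whether or not the gel does anything.

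The plan gives these tests the same threshold and the same multiplicity adjustment as the between-group tests, with no rule on which of them carries a claim. The p-values most likely to be small are thus the ones that say least about the gels. In G3 both sites receive a gel, so equal improvement on the two sides fits both gels working and also fits neither working. The plan gives no rule for reading that result.

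**Working it through.** **1. What the trial was sized for.** The Participants section uses a difference in clinical attachment level (CAL) at 3 months of 6.4 − 5.75 = 0.65, a variance of 0.35, 95% confidence and 80% power. The two-sample formula gives n = 2 × 0.35 × (1.960 + 0.842)² / 0.65² = 13.004, rounded up to 14 per group, which reproduces the stated figure. The sizing is for a difference between test and control sites. It gives no support to a within-group test.

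**2. What each contrast estimates.** Let S, H, R and G be the expected changes due to SRP, hygiene, regression to the mean and the gel.

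- Gel site, follow-up against baseline: S + H + R + G.
- SRP control site, follow-up against baseline: S + H + R.
- Difference in change between sites randomised within the patient: G.
- G3, flurbiprofen site minus aloe vera site: G(flurbiprofen) − G(aloe vera). S, H and R cancel, but neither G can be recovered alone.

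**3. How often an inert gel looks significant against baseline.**

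Inputs:
- n = 20 per group, from the plan.
- SD of change = √(2 × 0.35) = 0.84 mm. This takes the plan's variance and assumes no correlation between baseline and follow-up. The range tried is 0.59 (correlation 0.5) to 1.0.
- Common change S, assumed, because the documents give no size for it.
- Two-sided alpha 0.05 (sidedness is not stated).

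The test is a one-sample t-test of change with 19 degrees of freedom. Its noncentrality is S / (0.84/√20) = S / 0.188, so 2.66 at 0.5 mm and 5.32 at 1.0 mm. The critical value is 2.093 unadjusted. With Tukey over five visits it is 4.253/√2 = 3.007.

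| Assumed common change | Unadjusted | Tukey over five visits | All three groups, unadjusted / Tukey | Within-patient site contrast |
|---|---|---|---|---|
| 0.25 mm | 25% | 7% | 1.5% / 0.1% | 5% |
| 0.5 mm | 71% | 39% | 36% / 6% | 5% |
| 1.0 mm | 99.9% | 98% | 99.7% / 95% | 5% |
| 1.5 mm | 100% | 100% | 100% / 100% | 5% |

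The table comes from 20,000 simulated trials with an assumed between-site correlation of 0.5. The noncentral t calculation agrees with its single-group columns to within a percentage point.

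Sensitivity to the SD (0.59 to 1.0), with Tukey over five visits: 77% down to 26% at 0.5 mm, and 100% down to 91% at 1.0 mm. If the Tukey family is widened to 30 cells (three groups, two sites, five visits), the 1.0 mm figure runs from 99.6% down to 56%, and the 0.5 mm figure from 34% down to 5%.

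**4. Regression to the mean (secondary).** The calibration rule is that "both measurements at the baseline and after 24 hours were similar to one mm at the 90% level". Read as 90% of repeat differences within 1 mm, with normal errors, it gives an error SD of 1/1.645/√2 = 0.43 mm. For true site depth with mean μ and SD s, selection at an observed 6 mm or more gives an expected fall of 0.43²/√(s² + 0.43²) × φ(a)/(1 − Φ(a)), where a = (6 − μ)/√(s² + 0.43²).

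- μ = 5, s = 1.5: a = 0.641, ratio 1.246, fall 0.15 mm.
- μ = 3, s = 1.0: a = 2.756, ratio 3.057, fall 0.52 mm.

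These site distributions are assumptions. The result applies only if the analysed sites are the qualifying sites of 6 mm or more.

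**The case against.** The strongest reply is that the plan does not rest efficacy on within-group tests. The sentence on the mixed models covers between-group comparisons too, an ANOVA of group differences follows, the aim is comparative, and the sizing uses a between-site difference. This stands. A reader might infer that the sponsor intends to conclude efficacy from change over time, but nothing in the documents says so. What remains is that the plan does not rule it out and gives no order of importance.

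Second, *within each group* could include the test-against-control site comparison inside a patient group, which is the valid split-mouth contrast. That reading is possible, but the text describes change over time points and never names the site contrast.

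Third, a reader might infer that regression to the mean alone makes most groups significant. The documents do not support that. The 6 mm rule is a patient eligibility criterion, the analysed sites are not defined, and no site distribution is given. The additional CAL and radiographic criteria corroborate true depth, and the planned Tukey-Kramer adjustment lowers the rejection rate. Nor should the size of that fall be judged against the 0.65 difference used for sizing, which is a between-site CAL difference, not a change in probing depth.

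Fourth, a reader might see the lack of an SRP-only site in G3 as a design flaw. For the stated aim it is not: flurbiprofen against aloe vera within patients is a valid randomised contrast, and G1 and G2 supply the SRP reference.

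**Conclusion.** The concern holds as a fault of weight and specification. Within-group tests of change sit beside the randomised comparisons with equal standing, and they cannot show that a gel adds to SRP. The randomised site contrast, which can, is not named. With an assumed common SRP change of 1.0 mm and an SD of change of 0.84 mm, a wholly inert gel would be significant against baseline in about 98% of groups of 20 after Tukey over five visits. At 0.5 mm the figure is about 39%, and at 0.25 mm it is 7%, so the size depends heavily on the assumed SRP effect and on how wide the Tukey family is. The within-patient contrast holds its 5% throughout.

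The argument assumes that baseline precedes SRP, as Clinical measurements indicates. If it followed the initial SRP sessions, the SRP share would shrink, while continued healing, hygiene and any regression to the mean would remain. G3 alone cannot show that either gel adds to SRP. This should be corrected, but it does not invalidate the design.

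**What to change.** In the Statistical analysis section:

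1. Report within-group change descriptively (mean, SD, confidence interval) and take it out of the family of efficacy tests.
2. Base any claim that a gel adds to SRP on the within-patient difference in change, gel site minus SRP site, in G1 for flurbiprofen and in G2 for aloe vera. Include patient as a random effect and adjust for baseline, at one named outcome and time point.
3. Base the comparative claim on flurbiprofen minus aloe vera, within patient in G3.
4. State that a null G3 contrast is interpreted only alongside the G1 and G2 contrasts.

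The abstract describes a placebo in G1 and G2, while the Clinical protocol describes SRP as the control. These must be reconciled so that the reference in item 2 is clear.

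The cost is wording only, with no new data, visits or patients. The sponsor gives up within-group significance statements.
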